The primary objective of the proposed pilot clinical trial is to assess the feasibility and acceptability of delivering a diet counselling plus supplementation intervention to adult women with generalized anxiety disorder (GAD) as measured by recruitment, retention, and intervention uptake. The secondary objectives are to evaluate changes in anxiety symptom severity, quality of life, diet quality, mindful eating behaviours, self-efficacy, and biomarkers, over the intervention period as compared to the waitlist control period. This trial will lay critical groundwork for a larger, adequately powered clinical trial, designed to assess the effectiveness of dietary counselling in the management of GAD.

Trial Design and Setting

This pilot intervention study will recruit 50 adult women with moderate to severe GAD and provide a dietary counselling intervention in combination with an omega-3 supplement that also contains vitamin D. A randomized, waitlist-controlled design will be used (Figure 1). The waitlist-control design was selected to allow for random allocation to a non-treatment condition while still allowing all participants to complete the intervention. Waitlist-control designs have been suggested to improve rigor and preserve ethical considerations for studies where participant blinding is difficult(32). Twenty-five participants will be randomized to begin the intervention immediately and twenty-five participants will be randomized to observe a 12-week waitlist period before completing the intervention. This trial will take place at a single site. The study setting is the community clinic in the Canadian College of Naturopathic Medicine in Toronto, Canada. The study has been reviewed by the Research Ethics Board of the Canadian College of Naturopathic Medicine (CCNMREB040.[name]). Any amendments to this protocol will be communicated to the Research Ethics Board and Health Canada (the regulatory

authority for clinical trials in Canada) and modified on the trial registry. The design of this study involved participation from people with expertise in nutrition, psychiatry, research methods, laboratory testing, culinary education, behaviour changes, and lived experience with mental illness.

[figure not shown]

Figure 1: Diagram of participant flow through the trial

Participants Eligibility

Inclusion criteria:

1. A person aged 18-65 years who currently identifies as a woman.

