2. Primary diagnosis of generalized anxiety disorder based on a clinical interview with a psychiatrist using the Diagnostic and Statistical Manual of Mental Disorders (DSM-5) criteria.
3. Moderate to severe anxiety as defined as a Beck Anxiety Inventory score of 22 or higher.
4. Low quality diet as defined as a score of 8.5 or less on the MEDI-LITE tool.
5. All psychiatric medication, psychotherapy, and natural health products stable for the past four weeks.
6. Established therapeutic relationship with a family doctor, psychiatrist, or clinical psychologist as their primary source of mental health care.
7. Ability to swallow capsules.
8. Ability to read in English and provide informed consent.

Exclusion Criteria:

1. Currently meets DSM-5 criteria for obsessive-compulsive disorder, bipolar disorder, a psychotic disorder, an eating disorder, or substance use disorder based on clinical interview with a psychiatrist.
2. Current high level of suicidality assessed by trial psychiatrist using the Columbia Suicide Severity Scale.
3. Starting or changing the dose of a psychiatric medication, psychotherapy, or natural health products in the past four weeks.
4. Severe food allergies, intolerances or aversions that would prevent the individual from modifying their diet (includes aversion to bovine gelatin which is a component of the fish oil supplement).

5. Current participation in a program, research study or treatment plan involving diet or lifestyle modification.
6. Baseline Omega Score of >5% (suggesting adequacy of omega-3 fatty acids).
7. Supplementation of greater than 4000IU of vitamin D daily for at least one month in the previous six months.
8. Allergy to fish or any of the non-medicinal ingredients in the study product.

Participants who are assigned to the waitlist control, who do not meet one or more of the criteria at the time of starting the intervention will still be permitted to participate. This data will be included in the analysis. If a participant begins a new medication or psychotherapy, or adjusts the dosage, during the waitlist period, this new treatment must be stable for four weeks prior to beginning the treatment phase of the study, even if this requires extending the waitlist period by up to four weeks.

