Final Dietary Counselling Session	-discussion about achievements made during the program and affirmations -discussion of long-term goals and strategies to maintain
-----------------------------------	--

Dietary Supplement

During the 12-week study period, participants will be supplied with an omega-3 capsule supplement (AquaOmega High EPA) and instructed to take a dose of four capsules, once daily (containing a total of 3456 mg of omega-3 fatty acids: 2659mg of Eicosapentaenoic acid (EPA), 532mg of docosahexaenoic acid (DHA), and 800IU of Vitamin D), with a meal. Significantly more trials have been completed using omega-3 supplementation in the treatment of depressive disorders than anxiety disorders(42). Recent guidelines recommend a daily dose of 1-2g of EPA with a ratio of EPA:DHA of at least 2:1 for the treatment of depression(43). Due to the lack of specific recommendations on dose of omega-3 use for anxiety, our intervention will draw inference from these guidelines on depression to employ a dose that has been shown to be beneficial in other psychiatric disorders. We have selected a high dose, high EPA formula in order to maximize the likelihood of detecting a signal of effect in the present pilot trial.

Concomitant Therapies

All concomitant medication, psychotherapy or natural health products will be allowed during this trial. In order to minimize the risk of adverse events related to hypervitaminosis D, participants who are supplementing 1701 to 4000IU of vitamin D daily at the time of screening will be eligible to participate if they agree to decrease their vitamin D supplementation to 1700 so that their total daily intake of vitamin D, including the study product, is 2500IU. Participants will be encouraged to continue all other previous treatments at the same dose for the duration of the trial, if possible, but allowed to make changes if recommended by their mental health care provider. Participants will be queried at baseline

and at each follow up visit about their use of medication, psychotherapy or natural health products and any changes will be recorded, analyzed, and reported.

Safety and Criteria for Withdrawal

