will be measured before and after the waitlist period and the intervention period. Body mass index and change in weight during the intervention and control period will be calculated. These data will characterize the study participants and allow for assessment of confounding factors.

In order to assess changes in anxiety symptom severity, the Beck Anxiety Inventory, a validated, 21-item self-report inventory for measuring the severity of anxiety in participants with psychiatric illness, will be administered(49). The impact on quality of life will be assessed using PROMIS-29(50). In order to assess the impact of the intervention on behaviour change and qualitatively assess the acceptability of the intervention, questionnaires related to mindful eating and diet quality will be administered before and after the intervention. Mindful eating behaviours will be measured using Mindful Eating Questionnaire (MEQ) which has been validated for use in a diverse adult population(51). Changes in diet quality will be measured using the MEDI-LITE score, a concise tool for measuring consistency with the Mediterranean diet, which has been validated for use in adult populations(52). Changes in self-efficacy will be assessed using the General Self-Efficacy Scale(53). Changes in diet quality will also be assessed objectively through blood tests. Omega-3 fatty acids levels will be assessed using the dried blood spot test, Omega Score(54), which represents summed EPA, DHA and Docosapentaenoic acid as a percentage of the total fatty acids in whole blood. Analysis will be completed by Lipid Analytical Laboratories. Additional assessment will be completed to measure fasting serum cholesterol panel, markers of blood sugar levels and regulation (Hemoglobin, fasting insulin, fasting glucose and calculated HOMA-IR(55, 56)), vitamin C, beta-carotene, and C-Reactive Protein. These analyses will be completed by LifeLabs. Completion of the questionnaires and blood tests will be done at baseline, at the end of the waitlist control period (for participants assigned to this group) and at the end of the intervention. Participants who do not attend all of the scheduled visit but have not withdrawn will be contacted to complete the questionnaires and blood tests. See Supplemental File 4 for a summary of assessments on participant demographics, satisfaction with the dietary intervention, the research program, and participant experience.

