2. What did you not like, or like least, about participating in this study?
3. Which resources were most helpful? (examples: recipes, handouts, educational materials, videos etc.)
4. Which resources were least helpful?
5. Do you feel that your expectations were met during this study? Please explain.
6. Do you have any further comments related to the how the study was conducted? (ex. the processes, the questionnaires, etc.)
7. Were there any things that you liked about taking the Omega-3 supplement?
8. Were there any things that you did not like about taking the Omega-3 supplement?
9. How can we make this study better in the future?
10. Any other comments, concerns, or suggestions?

Supplemental File 5: Statistical analysis plan for the full-scale trial

For the full-scale trial, the primary outcome (Beck Anxiety Inventory) will be analyzed in a two-stage manner. All participants will be analyzed in the group to which they were randomized. First, the change

in anxiety will be compared between the active group and the waitlisted controls at the completion of the 12-week intervention for the active group. Between-group differences will be tested using an ANCOVA analysis that compares 12-week anxiety measures between groups while controlling for baseline anxiety measure. The change in anxiety score from just prior to the 12-week intervention to just afterwards will be summarized for all patients, waitlisted or not, who do receive the dietary intervention. This will permit a more precise estimate (smaller confidence interval) for the magnitude of the benefit while preserving the rigor of the randomized controlled trial. As a secondary analysis, the ANCOVA analysis will be repeated adjusting for age, income, education, food insecurity, smoking, body mass index, alcohol consumption and physical activity level.

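### When a wait is extended, the waitlist arm's single end-of-wait assessment cannot be both the 12-week control value and the value just before the intervention

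*Combined protocol and SAP*

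**What the plan says.** Under Trial Design and Setting, 25 of the 50 participants are "randomized to observe a 12-week waitlist period before completing the intervention". The text after the exclusion criteria (Participants Eligibility) then provides for treatment changes. The trigger is a post-randomisation event in this arm: "If a participant begins a new medication or psychotherapy, or adjusts the dosage, during the waitlist period". The requirement attached to it is that "this new treatment must be stable for four weeks prior to beginning the treatment phase of the study". A later start is accepted as the price of this, "even if this requires extending the waitlist period by up to four weeks".

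Outcomes Measured places questionnaires and blood tests at baseline, "at the end of the waitlist control period (for participants assigned to this group) and at the end of the intervention". The schedule in Supplemental File 2 gives the waitlist arm one set of entries between baseline and close-out. They stand in the end-of-wait column, printed as Day 85, and the first counselling session follows on Day 86. There is no visit window and no column for an extended wait.

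Under Concomitant Therapies, participants in either arm are "allowed to make changes if recommended by their mental health care provider", and such changes are to be recorded, analysed and reported. No matching delay of the outcome is described for the immediate-start arm.

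Supplemental File 5, the analysis plan for the full-scale trial, uses two quantities. The first is an ANCOVA that "compares 12-week anxiety measures between groups while controlling for baseline anxiety measure". The second is summarised over everyone who receives the intervention: "The change in anxiety score from just prior to the 12-week intervention to just afterwards".

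**The concern.** In an unextended wait the 12-week control score and the pre-intervention score are the same measurement, taken on Day 85 with the first session a day later. The extension rule pulls them apart, but the plan still provides only one measurement. Two readings are possible, and each spoils a different quantity.

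- **The assessment follows the wait.** The control value is then taken up to 28 days late. This happens in one arm only, in people selected by an event after randomisation that is plausibly related to symptoms, and after four stable weeks on the new treatment. If the new treatment helps, controls look better and the between-arm difference shrinks.
- **The assessment stays at Day 85.** The between-arm comparison is then intact, but the pre-intervention value is up to 28 days old. Any gain from the new treatment during the extension is credited to the diet and supplement programme, so the pre-post change is inflated.

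The two distortions run in opposite directions. If staff decide case by case, the result cannot be interpreted in either direction. Recording the treatment change identifies the affected participants but does not supply a score that was never collected.

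**Working it through.** **The plan's own figure.** A 12-week wait ends on Day 12 × 7 + 1 = 85, which agrees with the schedule.

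**Maximum extension.** 85 + 28 = Day 113, or 12 + 4 = 16 weeks, with the first session on Day 114 instead of Day 86. Follow-up is at most 28/84 = 33% longer.

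**Who is extended.** Four stable weeks are needed before the start, so for a single change at wait week w the extension is max(0, w + 4 − 12) weeks, at most 4.

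| Week of change | Extension (weeks) | End of wait (week) |
|---|---|---|
| 8 or earlier | 0 | 12 |
| 9 | 1 | 13 |
| 10 | 2 | 14 |
| 11 | 3 | 15 |
| 12 | 4 | 16 |

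Only changes after about week 8 matter, and 16 weeks is reached only by a change at the very end.

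**Share extended.** The documents give no rate of treatment change. Assume that 10–30% of controls change once, evenly over the 12 weeks. The last four weeks hold 4/12 = 1/3 of the changes:

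- 0.10 × 1/3 = 3.3% of controls, or 0.8 of 25
- 0.30 × 1/3 = 10% of controls, or 2.5 of 25

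**Shift in the arm mean.** Shift = share extended × further BAI change during the extension. With an assumed 3–6 points per extended participant:

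- low: 0.033 × 3 = 0.1 points
- high: 0.10 × 6 = 0.6 points

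Under the same assumption the average extension is two of the four weeks. If the further change scales with the length of the extension, the range halves to about 0.05–0.3 points.

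Under the first reading this is the shift in the control mean. Under the second it is the shift in the waitlist arm's pre-post change. In the pooled pre-post change over both equal arms it is half as large, 0.05–0.3 points before any scaling for length.

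**Against sampling error.** The standard error of a 25 v 25 difference is SD × √(2/25). For an assumed SD of 8 to 12 this is 2.3 to 3.4 points, well above the shift. The standard error falls as the sample grows, but the shift depends only on the share extended and the change per person, so it does not.

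**The case against.** The strongest reply is that the schedule prints Day 85, and that Supplemental File 5 sets the between-group comparison at the end of the active group's 12 weeks. A reader might infer from the extension rule that the control outcome is in fact taken at up to 16 weeks. The documents do not establish that. Day 85 is a tenable reading, and under it the randomised comparison is sound. But that column is labelled as the end of the wait and is paired with a Day 86 start that an extended participant cannot meet, so the text does not settle the matter. Nor would declaring Day 85 to govern be enough, because the pre-intervention value would then be out of date.

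A second reply is that the 12-week ANCOVA belongs to another trial. This stands. The pilot's primary outcome is feasibility and acceptability, its analysis is descriptive, and its secondary objective compares change over periods and names no week. It would be wrong to infer that a primary result of this pilot is biased.

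A third is that few people are affected. This also stands. A reader might take 10–30% of controls as extended and arrive at up to 0.30 × 6 = 1.8 points. With changes spread evenly over the wait, 30% extended would need 0.30 ÷ 1/3 = 90% of controls to change treatment, although all entered after four stable weeks. That is not credible.

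Finally, the contrast between arms should not be overdrawn. The immediate arm's close-out is printed as Day 85 or later, so its timing is not tightly fixed either. A treatment change also affects a Day 85 score in either arm; the extension only adds to that.

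**Conclusion.** The defect is real but minor. It follows from the text and needs no assumed number: one measurement is asked to supply two quantities that the extension rule separates by up to 28 days, so in every extended participant one of them is mistimed.

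In this pilot the effect is confined to descriptive secondary outcomes. It is probably about 0.1–0.6 BAI points in the waitlist arm's mean, given 10–30% of controls changing treatment once, evenly over the wait, and 3–6 further points each. All of these inputs are assumptions. The direction depends on the reading and on the new treatment being helpful. None of the feasibility or acceptability criteria depends on when this score is taken.

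The reason to act now is that the pilot is meant to prepare the full-scale trial, whose plan uses both quantities and has no term for assessment time. If the rule is carried over unchanged, a larger sample will not remove the distortion.

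**What to change.** Reconcile Participants Eligibility, Outcomes Measured and the Supplemental File 2 schedule as follows:

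- Assess every waitlist participant at Day 85, whether or not the wait is extended, and use that value in the between-arm comparison.
- When the wait is extended, repeat the online questionnaires just before the first counselling session and measure weight at that visit, which is already in person. Use these as the pre-intervention values.
- Report actual assessment days in both arms.
- State that pre-intervention blood values in extended participants come from Day 85 and may be up to 28 days old. The proposal does not add a second blood draw.

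Carry the same wording into the full-scale plan. The stability and extension rule is left as it is.

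The cost is a few sentences, one added schedule column, and one extra online questionnaire set for what is likely to be no more than two or three participants. If the end-of-wait weight was meant to be taken at the first session, extended participants would also need a separate Day 85 attendance. The documents do not say.

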As rescue medicine, participants will be advised to take the over-the-counter product, diphenhydramine (Benadryl), in the event of an allergic reaction to the study product or any of the new foods that they consume, as recommended on the product label. Diphenhydramine will be provided to participants with the study product. Participants will be queried about use of the rescue medication and asked to return any unused product at the end of the trial. The use of rescue medication for an allergic reaction will be recorded. Participants will be instructed to contact the study coordinator immediately if they experience a negative reaction to the study product or a serious worsening of their health. They will be provided with an email and phone number for this purpose. The qualified investigator will assess the patient and recommend a course of action. If the participant requires medical visits or medications that are not reimbursed by the Ontario Health Insurance Plan (OHIP), these costs will be reimbursed by the study sponsor, the Canadian College of Naturopathic Medicine. At each study visit, participants will be asked if they have experienced any negative effects since beginning the study product. Participants will be withdrawn from the study if they experience an allergic response, or other serious adverse event, as a result of the study product. These participants will be referred to their primary health care provider or a walk-in clinic for management. Participants will also be withdrawn if the trial psychiatrist deems the participant not adequately stable to continue to participate in the trial. This includes the presence of severe suicidal ideation or symptoms of psychosis. At each follow up visit, participants will be asked by the intervention deliverer if they have experienced a significant worsening in their mental health since the previous visit. If they report symptoms related to suicidal ideation, the Ask Suicide-Screening Questionnaire (ASQ) will be completed(44). If the participant screens positive, they will be referred to

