the study psychiatrist for a complete assessment. If they screen acute positive, they will be referred directly to a crisis center or the hospital emergency room. If they report any symptoms related to psychosis (any report of hallucinations, delusions, or disordered thinking), the participant will be referred to the study psychiatrist for assessment. If they meet criteria for withdrawal, they will be referred to their current mental healthcare provider for appropriate assessment and treatment. If a participant reports a significant worsening in symptoms of anxiety or depression, they will be permitted to remain enrolled in the study. They will be encouraged to contact their primary mental health care provider for assessment and management. If the mental health care provider suggests that psychiatric rescue medication is needed, this clinician will recommend the treatment to the participant. If rescue medication is used for mental health symptoms, participants will be allowed to continue participating in the study. The use of rescue medication will be queried at each study visit and recorded. Given that the primary objective is feasibility and acceptability, participants with poor compliance with the study intervention will not be withdrawn from the study.

Expected adverse events for this study product include fishy aftertaste, bad breath, heartburn, nausea, or loose stools, atrial fibrillation, increased bleeding. All adverse events will be recorded, and these records will be maintained for 15 years. The clinical trial sponsor will inform the Natural and Non-prescription Health Product Directorate of Health Canada of any serious expected or unexpected adverse events related to the study product immediately if possible and no later than seven days after becoming aware of the information. Serious adverse events will also be reported to the Research Ethics Board that has reviewed the study protocol.

Participants will be withdrawn from the study if their baseline serum levels of 25-hydroxy-vitamin-D is greater than 120 nmol/L, as this level has been associated with safety concerns(45). These individuals will be instructed to contact their primary health care provider for assessment and management. In the event that the baseline or final blood work assessment suggests the presence of an undiagnosed

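### A participant who reports worsening anxiety or depression at a visit, but nothing about suicidal ideation, gets no suicide screen and has no stated route to the trial psychiatrist

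*Combined protocol and SAP*

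**What the plan says.** All of the follow-up procedure is in Safety and Criteria for Withdrawal. At each follow-up visit, "participants will be asked by the intervention deliverer if they have experienced a significant worsening in their mental health since the previous visit". The stated responses are:

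- **Ideation.** "If they report symptoms related to suicidal ideation, the Ask Suicide-Screening Questionnaire (ASQ) will be completed(44". A positive screen goes to the study psychiatrist, and an acute positive goes straight to a crisis center or emergency room.
- **Psychosis.** Any reported symptom goes to the study psychiatrist.
- **Worse anxiety or depression.** "If a participant reports a significant worsening in symptoms of anxiety or depression, they will be permitted to remain enrolled in the study". Then: "They will be encouraged to contact their primary mental health care provider for assessment and management".

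The trial psychiatrist may withdraw a participant judged too unstable to continue. On that ground the plan adds: "This includes the presence of severe suicidal ideation or symptoms of psychosis".

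A separate route starts with the participant. If she contacts the coordinator about a serious worsening of her health, "The qualified investigator will assess the patient and recommend a course of action".

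At entry, the trial psychiatrist interviews each candidate and applies the Columbia scale (Pre-study Screening, Randomization and Baseline Evaluation). Only a high level of suicidality excludes. Co-morbid depression is allowed, and every participant must have a treating clinician (Participants Eligibility).

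**The concern.** The ASQ is a screening tool, but the plan uses it only after the participant has raised the subject it screens for. Someone who says her depression is much worse, and says no more, need not be asked about suicidal thoughts. The psychiatrist's withdrawal decision depends on information that this branch does not collect.

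Lower-level or new ideation during the trial is possible. Participants have GAD with a Beck Anxiety Inventory score of 22 or more, may also be depressed, and are excluded only for high suicidality. Four of the six follow-up sessions are planned by video, since only the first, fourth and seventh sessions are in person (The Intervention). What is at stake is participant safety. No sample size, error rate or planned summary is affected.

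**Working it through.** The plan gives no figure to reproduce here, so the check has two parts: a trace of the branches and a bound on the workload of the remedy.

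**Branch trace**

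| Reported at the visit | ASQ required? | Stated route to trial psychiatrist |
|---|---|---|
| Ideation-related symptoms, with or without worsening | Yes | Yes, if positive (acute positive: crisis center or emergency room) |
| Psychosis symptoms | No | Yes |
| Worse anxiety or depression only | No | None |

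The branches are not exclusive. A participant with worsening depression who mentions anything related to ideation does get the ASQ. The gap is the last row.

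The rest of the document does not fill it:

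- The Columbia scale is an entry procedure.
- The schedule in Supplemental File 2 lists no suicidality measure after entry. An event-triggered ASQ would not appear there in any case, so the text on triggers is what counts.
- Treatment changes are queried at follow-up visits (Concomitant Therapies), and for rescue medication: "The use of rescue medication will be queried at each study visit and recorded". Neither query asks about suicidality.
- The visit question on negative effects is framed around the study product.
- The participant-initiated route is not linked to the visit question, and the qualified investigator is not identified as the trial psychiatrist.

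**Workload bound**

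Inputs from the documents: 50 participants (Trial Design and Setting); 7 sessions of 45 to 60 minutes (The Intervention).

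- Follow-up sessions per participant: 7 - 1 = 6.
- Maximum follow-up visits: 50 x 6 = 300, at full attendance.
- Follow-up session time: 300 x 45 = 13,500 minutes to 300 x 60 = 18,000 minutes.

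Assumed, not in the documents: worsening reported at 5%, 10% or 20% of visits; 2 to 5 minutes per ASQ; 10% to 30% of added screens positive.

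| Worsening reported | Added ASQs (at most) | Minutes | Positive screens |
|---|---|---|---|
| 5% | 300 x 0.05 = 15 | 30 to 75 | 1.5 to 4.5 |
| 10% | 300 x 0.10 = 30 | 60 to 150 | 3 to 9 |
| 20% | 300 x 0.20 = 60 | 120 to 300 | 6 to 18 |

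Share of follow-up session time: from 30 / 18,000 = 0.17% to 300 / 13,500 = 2.2%.

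The counts are upper bounds. Some of these participants would trigger the ASQ already, and a change made part-way through reaches only the visits still to come.

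**The case against.** The strongest reply is that the scheme is tiered on purpose. The plan requires a treating clinician precisely so that a participant who seriously worsens has adequate care, and it sends worsening anxiety or depression to that clinician. Ideation, psychosis and acute risk each have a stronger response. Sessions are individual and run by a practitioner with more than 10 years of experience in dietary counselling for people with mental health concerns. Nothing forbids that practitioner from probing, giving the ASQ or calling the psychiatrist. On this view a lower threshold for the ASQ is a preference.

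Much of this stands. The safeguards are real, the text contains no contradiction, and the referral to the treating clinician should stay. But contact with that clinician is only encouraged, no step confirms that it happened, and discretion to probe is not a requirement to ask.

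Three further points are fair:

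- The workload figures say nothing about harm avoided.
- The ASQ citation is to a pediatric emergency setting, so its accuracy in these adults, and the number of false positives, are unknown.
- A worsened participant who screens negative would still have no stated route to the psychiatrist. She would have been asked, however, and a positive screen opens the route.

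**Conclusion.** The concern holds. By the plan's own text, worsening anxiety or depression reported without ideation-related or psychotic symptoms leads neither to the ASQ nor to the trial psychiatrist. This conclusion rests on the wording alone and needs no assumed rate.

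The size of the safety benefit cannot be computed, because the documents give no figures for ideation, disclosure or reported worsening. The burden of closing the gap is small across the assumed ranges: at most 15 to 60 added screens, about 0.2% to 2.2% of follow-up session time, and about 2 to 18 referrals. The sponsor should make the change as an inexpensive improvement. Confidence is medium, because existing safeguards may already prompt disclosure in some cases.

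**What to change.** Widen the trigger in Safety and Criteria for Withdrawal, for example: *The ASQ will be given to any participant who reports significantly worse mental health, or who reports ideation-related symptoms.* Keep the existing positive and acute-positive routes, and keep the advice to contact the treating provider.

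**Cost.** One changed sentence and a briefing for the intervention deliverer. No new instrument, visit or referral route is needed. Screening had already produced early results (Participants Eligibility), so this would be a mid-trial amendment: "Any amendments to this protocol will be communicated to the Research Ethics Board and Health Canada", with the registry entry changed as well. Running cost, under the assumptions above, is 30 to 300 minutes of existing session time plus the added referrals.

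**Limits.** The change does not reach participants who deny worsening. It adds nothing during the 12-week wait, when no counselling sessions are held. ASQ answers remain self-reported.
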